## Specific Changes Implemented in Current Version

Description of Change	Brief Rationale
1. Include MBSR classes that are offered at locations in addition to UCSF Osher Center	1. A significant challenge is that the UCSF Osher Center does not offer MBSR frequently, and the classes fill up quickly. Currently, the number of eligible RISE Study participants exceeds the available spots in the Osher MBSR class. Additionally, we have had otherwise eligible study participants who were unable to participate because they were not available at the particular time of the Osher MBSR class
2. Add recruitment sources	2. To enable rapid identification of eligible participants and to maximize likelihood that we can achieve our anticipated accrual rate. We are having a lower yield from our Facebook ads compared to our previous studies. We are adding recruitment sources that we found helpful in previous studies, such as parenting listservs and social media posts
3. Remove Epworth Sleepiness Scale	3. Initially we planned to use the Epworth to screen for narcolepsy. The Epworth has excluded 10% of respondents on our screener. Narcolepsy has a base rate of 0.05%. Thus, it is highly implausible that 10% of respondents had narcolepsy. Instead we believe the Epworth is identifying people with normative pregnancy-related sleepiness. Additionally, this measure is redundant with an item that assesses whether participants have been diagnosed with narcolepsy
4. Increase the gestational age range from 12-28 to 8-28.	4. We have had several potential participants who are experiencing significant sleep disruption, are interested in participating, but are less than 12 weeks pregnant (and will be too far along in their pregnancy for the next available MBSR course). This wider gestational age range is similar to our previous research, in which we evaluated digital CBT for prenatal insomnia, and enrolled participants at any point in pregnancy up until 28 weeks

## STATEMENT OF COMPLIANCE

The trial will be conducted in accordance with International Council on Harmonisation Good Clinical Practice (ICH GCP), applicable United States (US) Code of Federal Regulations (CFR), and the National Center for Complementary and Integrative Health (NCCIH) Terms and Conditions of Award. The Principal Investigator will assure that no deviation from, or changes to the protocol will take place without prior agreement from the funding agency and documented approval from the Institutional Review Board (IRB), except where necessary to eliminate an immediate hazard(s) to the trial participants. All personnel involved in the conduct of this study have completed Human Subjects Protection and ICH GCP Training.

The protocol, informed consent form(s), recruitment materials, and all participant materials will be submitted to the IRB for review and approval. Approval of both the protocol and the consent form(s) must be obtained before any participant is consented. Any amendment to the protocol will require review and approval by the IRB before the changes are implemented to the study. All changes to the consent form(s) will be IRB approved; a determination will be made regarding whether a new consent needs to be obtained from participants who provided consent, using a previously approved consent form.

## 1 PROTOCOL SUMMARY

### 1.1 SYNOPSIS

Title:	Randomized controlled trial of mindfulness-based stress reduction plus prenatal sleep supplement versus usual care: Acceptability, feasibility, and adherence
Grant Number:	K23AT009896
Study Description:	The goal of this trial is to conduct a pilot randomized controlled trial to evaluate mindfulness-based stress reduction plus prenatal sleep supplement to improve prenatal sleep (MBSR + PS) compared to treatment as usual (TAU). Our primary focus is on evaluating acceptability, feasibility, and adherence. Secondly, we will explore condition differences in hypothesized targets (i.e., psychological responses to nightly physical symptoms) and the clinical outcome of interest (i.e., subjective sleep quality).
Objectives:	Primary Objectives: Acceptability, feasibility, adherence Secondary Objectives: Change in psychological responses to nightly physical symptoms; between group differences in global sleep quality
Endpoints:	Primary Endpoint: Willingness to be randomized, treatment initiation, reasons for attrition, satisfaction; Yield of eligible participants, number randomized, retention rate, completeness, missingness; Session attendance, home practice completion Secondary Endpoints: 14-day daily diary, validated retrospective measures of psychological constructs hypothesized as mediators; subjective sleep quality 50 women 12-28 weeks gestation with poor sleep quality
Study Population:	50 women 12-28 weeks gestation with poor sleep quality
Phase:	Stage 1B in the NIH Stage Model for behavioral intervention development
Description of Site Enrolling Participants:	Single site study at University of California, San Francisco.
Description of Study Intervention:	The study intervention is standard mindfulness-based stress reduction (MBSR). The supplemental prenatal sleep content draws material from mindfulness-based therapy for insomnia, mindfulness-based childbirth and parenting program, and cognitive behavior therapy for prenatal insomnia.
Study Duration:	12 months
Participant Duration:	Approximately 3 months

## 1.2 SCHEMA

### ***Flow Diagram***

### 1.3 SCHEDULE OF ACTIVITIES

Timepoint	Screening	Baseline	Daily	Weekly	Endpoint
Allowable window	N/A	0-4 weeks prior to randomization	Within 24 hours	Within 3 days	+/- 4 weeks
Screening consent	x				
Screening measures	x				
Demographic form	x				
Orientation session	x				
Study consent	x				
14-day daily diary		x			x
Outcome measures		x			x
Depression measure				x	
Home practice measure (MBSR+PS only)			x		
Sleep diary (MBSR+PS only)			x		
Use of non-study treatments questionnaire		x			x
Adverse events questionnaire					x
Client Satisfaction Questionnaire					x

## 2 INTRODUCTION

### 2.1 STUDY RATIONALE

Poor sleep quality is highly prevalent during pregnancy, with important implications for maternal and infant health and well-being. That is, poor sleep is associated with increased risk of: depression; suicidal ideation; gestational diabetes; preterm birth; and caesarean birth. Despite this, there is limited research on interventions to improve prenatal sleep, and prior research did not target the specific factors contributing to poor sleep quality in this population.

Specifically, pregnant women report that physical symptoms, including discomfort and pain, disturb their sleep. In non-pregnant populations, the pain-sleep relationship is bidirectional, and maladaptive psychological responses to pain further exacerbate poor sleep. Although pregnancy-related discomfort and pain may be difficult to eliminate, psychological responses to such symptoms offer modifiable targets to break the pernicious discomfort/pain – poor sleep cycle.

Theory and empirical evidence indicate that mindfulness-based interventions may be effective for targeting these psychological responses. For example, mindfulness-based stress reduction (MBSR) teaches skills to accept difficult, unchangeable experiences (like chronic pain), and randomized controlled trials demonstrate improvements in sleep and responses to pain in non-pregnant populations. MBSR has been adapted to teach skills for coping with intense sensations during pregnancy and birth (mindfulness-based childbirth and parenting, MBCP) and to improve sleep among individuals with chronic insomnia (mindfulness-based therapy for insomnia, MBTI). However, there is a paucity of research optimizing and evaluating mindfulness-based interventions for improving prenatal sleep quality.

The goal of this trial is to conduct a pilot randomized controlled trial to compare a program consisting of MBSR plus prenatal sleep content (MBSR+PS) to treatment as usual (TAU). Our primary focus is on evaluating acceptability, feasibility, and adherence. Secondarily, we will explore condition differences in hypothesized targets (i.e., psychological responses to nightly physical symptoms) and the clinical outcome of interest (i.e., subjective sleep quality).

### 2.2 BACKGROUND

Poor sleep quality during pregnancy is common and associated with negative correlates and consequences for mom and baby. Over 75% of pregnant women report poor sleep quality, which is linked to adverse psychological and obstetric outcomes, such as increased risk of depression symptom severity, suicidal ideation after accounting for depression, gestational diabetes mellitus, preterm birth, and caesarean birth. Moreover, prenatal poor sleep quality often persists into the postpartum period, thereby maintaining and exacerbating postpartum depression. Thus, improving poor sleep quality during pregnancy may have significant health implications for both mother and offspring.

Pregnant women report that pregnancy-related physical symptoms, including discomfort, back pain, and hip/pelvic pain, disturb their sleep. Longitudinally, such symptoms predict worsening sleep quality. In non-pregnant populations, the pain-poor sleep association is bidirectional, and poor sleep exacerbates discomfort and pain. It may be challenging to eliminate pregnancy-related discomfort and pain, but psychological responses are modifiable targets to break the pain/discomfort-poor sleep cycle. In studies of individuals with chronic pain, acceptance of pain predicted lower insomnia severity, after accounting for pain severity, and presleep rumination about pain was associated with longer sleep latency, after accounting for pain severity. Our preliminary data in a sample of 50 pregnant women indicated that physical symptoms were the most common reason women had trouble falling or staying asleep, relative to difficulties quieting the mind, other, or unknown. The psychological responses that had the strongest associations with sleep quality were: “I felt annoyed or bothered by my physical symptoms” ( $r = -0.29$ ), “I reassured myself that my symptoms were normal” ( $r = 0.17$ ), and “I paid attention to my physical symptoms without trying to change them” ( $r = 0.16$ ).

Current options for improving prenatal sleep are limited, but pregnant women want help. There is limited research on acceptable and effective interventions to improve sleep during pregnancy. Prescription medications, such as zolpidem, may be associated with increased risk of adverse birth outcomes and pregnant women prefer non-pharmacological interventions for sleep. The small body of research examining non-pharmacological interventions for improving sleep during pregnancy have used cognitive behavioral approaches to treat chronic insomnia. Such approaches target dysfunctional sleep beliefs and behaviors, but do not target the unique factors contributing to poor sleep quality during pregnancy. Previously, we found that significantly more pregnant women with insomnia who were randomized to digital cognitive behavior therapy for insomnia experienced remission in insomnia symptoms relative to women randomized to standard care; however, most women continued to experience at least subthreshold symptoms. Thus, targeting pregnancy-specific sleep disturbances, such as nocturia and discomfort, may help more women achieve symptom remission. Mindfulness-based and acceptance-based approaches that focus on increasing acceptance of physical symptoms that may be difficult to eliminate may be particularly well suited for pregnancy-related poor sleep. Taken together, these data emphasize the need for alternative approaches to improving prenatal poor sleep quality by addressing key mechanisms.

Mindfulness-based intervention may be a promising approach for improving pregnancy-related factors of poor sleep quality. Mindfulness-based stress reduction (MBSR) was developed to reduce psychological reactivity to chronic pain. In a group intervention, MBSR participants learn skills to notice and accept difficult, often unchangeable, sensations, emotions, and thoughts. Randomized clinical trials of MBSR among non-pregnant populations demonstrate significant effects on the psychological mechanisms (pain acceptance and rumination) that we hypothesize contribute to poor sleep quality during pregnancy, as well as on objective and subjective measures of sleep, even in the context of chronic pain. Additionally, mindfulness-based therapy for

insomnia (MBTI) is effective for improving sleep among individuals with chronic insomnia.

Nearly a quarter of pregnant women report using mind-body practices, and more pregnant women prefer mind-body intervention to pharmacotherapy for improving sleep. However, there is a paucity of research optimizing and evaluating a mindfulness-based intervention for improving sleep during pregnancy. The current trial seeks to address this critical gap. Improving sleep quality during pregnancy has the potential to avert its myriad negative consequences, with considerable implications for women and their families.

## 2.3 RISK/BENEFIT ASSESSMENT

### 2.3.1 KNOWN POTENTIAL RISKS

**MBSR+PS:** Participation in the study intervention carries minimal risk of emotional discomfort. It is possible that participants may experience injury or discomfort during mindful stretching and walking practice; however, such practices may also improve pain during pregnancy. Previous studies of mindfulness-based interventions, including in pregnant populations, demonstrate safety and acceptability, with no adverse events reported. Some participants may be advised to implement techniques designed to consolidate sleep. These techniques reduce the amount of time spent awake in bed, which increases sleep drive, and ultimately decreases sleep onset latency and wake after sleep onset. Participants may experience temporary increases in sleepiness during this component of treatment. Two previous trials that included this technique among pregnant women found no unanticipated serious adverse events. We are aware of no research to suggest that the proposed intervention would confer risk to fetal, obstetric, or infant outcomes. At this time, there is a paucity of other treatments specifically for pregnancy-related poor sleep quality. Pharmacotherapy is associated with adverse birth outcomes, and pregnant women prefer non-pharmacological treatments. Cognitive behavior therapy targets maladaptive sleep beliefs and behaviors that are unique to chronic insomnia, and it does not address pregnancy-related factors of poor sleep quality.

**Self-report questionnaires:** There are no known risks for completing the study questionnaires, though it is possible that participants may experience temporary discomfort from thinking about their physical symptoms, psychological responses, and sleep.

**Actigraphy (optional depending on COVID-19 guidelines; see Section 8.1):** There is no risk of injury from the wrist-actigraph to measure sleep, though it may feel like a slight inconvenience wearing a wrist device for 14 days. There may be a risk of allergy to the metal of the actigraph device.

**Confidentiality of data:** Although every reasonable effort will be taken, confidentiality on web-based surveys cannot be guaranteed. It is possible that information may be captured and used by others who are not associated with this study.

**Inconvenience:** There may be some burden associated with completing the questionnaires and attending intervention sessions.

**Worsening depressive symptoms and/or suicidal ideation:** As is true for non-perinatal individuals generally, participants with poor sleep quality may experience increases in depressive symptoms and/or suicidal ideation, independent from their involvement in the study.

### 2.3.2 KNOWN POTENTIAL BENEFITS

Previous research suggests that mindfulness-based interventions are associated with improvements in sleep and responses to pain in non-pregnant populations. All participants may benefit from ongoing monitoring of and referral for depression incidence or suicidality. In the long-term, there are substantial benefits to be gained by optimizing a mindfulness-based intervention to improve prenatal sleep.

### 2.3.3 ASSESSMENT OF POTENTIAL RISKS AND BENEFITS

**MBSR+PS** Participants will be provided with a thorough description of the intervention prior to randomization, and notified that they can withdraw participation at any time without penalty. Given the physical and psychological consequences of poor sleep quality during pregnancy, we expect that the proposed intervention would be associated with improved outcomes. However, important precautions will be taken to minimize physical risks. Participants will be provided the American College of Obstetrics and Gynecology list of indicators to terminate exercise. Participants will be advised to stop the physical activity if these signs are present, and to contact their obstetric health care provider. We will ask participants to alert us if they experience an increase in daytime sleepiness, and will advise them about the risks of driving or doing any activity where severe sleepiness puts them at danger, and will instruct them to take naps if they feel sleepy.

**Self-report questionnaires:** Participants will be allowed to skip any questions they do not feel comfortable answering. One exception is that participants will be informed during the initial screening that skipping questions that are necessary for determining eligibility may preclude their ability to participate in the study. Additionally, because all questionnaires will be completed online, participants can complete them in a location and at a pace that feels comfortable to them.

**Actigraphy (optional depending on COVID-19 guidelines; see Section 8.1):** In case of allergy, participants can wear the monitor over their sleeve or use a wrist sports sweatband to protect their skin.

**Confidentiality:** All data will be handled with the utmost attention to participants' confidentiality. Participants will be assigned unique, coded, confidential identifiers that will be used to label all data forms, data entries, and questionnaires. The key linking the participants' identity to their unique coded identifier will be stored on a cloud-based collaboration tool that uses access controls and encryption, and is safe for storing protected health information. Access to all data will be limited to the PI and trained,

authorized study staff.

One limit to confidentiality is if a participant indicates she is at imminent risk of harming herself. If a participant endorses PHQ-9 item 9, a pop-up will immediately appear with instructions to call 911 or go to the nearest emergency room for a life-threatening emergency. Additionally, email triggers will immediately notify study staff, who will call to conduct a risk assessment using the Columbia-Suicide Severity Rating Scale (C-SSRS). At the beginning of the C-SSRS assessment, study staff will ask the participant for her current location. Study staff will provide psychological referrals for low to medium risk. For immediate risk, the study staff will direct the participant to the nearest emergency room and/or to call 911. If the participant declines, the study staff will call the participant's local emergency services number, which will be recorded in the participant tracking database at enrollment. Study staff will immediately notify Co-Investigator [name], a psychiatrist with experience working with depressed and suicidal individuals, anytime a participant endorses suicidality. He will provide further supervision as deemed necessary and will determine whether additional follow-up assessment is indicated. Principal Investigator [name], a licensed clinical psychologist with experience working with depressed perinatal women, will be a back-up if [name] is unavailable.

**Worsening depressive symptoms:** Participants will be instructed to make immediate contact with study personnel with any questions or concerns regarding worsening depression symptoms. At enrollment, we will provide contact information for [name], [name], therapeutic resources, and crisis hotlines. We will closely monitor depressive symptom severity via weekly administration of the PHQ-9. Study staff will recommend that any participant who scores above the PHQ-9 cutoff ( $\geq 10$ ) notify her obstetrician. Additionally, study staff will recommend that participants who score above the cutoff seek treatment for depression and will provide local resources using the Postpartum Support International "Find Local Support and Help" resource (<https://www.postpartum.net/get-help/locations/>).

**Inconvenience:** Every effort will be taken to reduce participant burden, and participants will be compensated for their time and effort.

### 3 OBJECTIVES AND ENDPOINTS

OBJECTIVES	ENDPOINTS	JUSTIFICATION FOR ENDPOINTS	METRIC
Primary			
To determine acceptability	
 
1. Willingness to be randomized
 
2. Treatment initiation
 
3. Reasons for attrition
 
4. Satisfaction
 
	One of the primary study objectives of this pilot RCT is to determine the acceptability of the MBSR+PS intervention and the study procedures.	
 
1. Among women determined to be eligible to participate, we aim for <math>\geq 80\%</math> to indicate willingness to be randomized
 
2. We aim for <math>\geq 85\%</math> MBSR+PS participants to attend at least one session of MBSR and the PS supplement
 
3. Assessed qualitatively
 
4. Among participants randomized to MBSR+PS, we aim for a total score <math>\geq 24</math> on the Client Satisfaction Questionnaire
 

To determine feasibility	
 
1. Yield of eligible participants
 
2. Number randomized
 
3. Retention rate
 
	One of the primary study objectives of this pilot RCT is to determine the feasibility of the MBSR+PS intervention and	
 
1. Defined as # Eligible / # Assessed for Eligibility
 
2. N=50 within study timeline
 

OBJECTIVES	ENDPOINTS	JUSTIFICATION FOR ENDPOINTS	METRIC
	
4. Completeness
 
5. Missingness
	
the study procedures.
	
3. Our goal is for <math>\geq 80\%</math> of randomized participants to complete endpoint measures
 
4. For a measure to be considered complete, at least 95% of items must be completed. We aim for <math>\geq 95\%</math> of participants who are participating at a particular time point to complete each scale
 
5. Explore patterns of incomplete data and investigate possible missingness mechanisms (i.e., missing completely at random, missing at random, missing not at random).

To determine adherence	
1. Session attendance
 
2. Home practice completion
	
One of the primary study objectives of this pilot RCT is to determine participant
	
1. We aim for an average of at least 50% of MBSR and PS supplement

OBJECTIVES	ENDPOINTS	JUSTIFICATION FOR ENDPOINTS	METRIC
		adherence to the MBSR+PS intervention.	
sessions attended.
 
2. We will examine the frequency and duration of formal and informal practices

Secondary/Exploratory			
To explore evidence of change in psychological mediators	
 
14-day daily diary
 
Validated retrospective measures of psychological constructs hypothesized as mediators
 
	A secondary study objective is to explore group differences in change on potential mechanistic outcomes.	Non-acceptance, avoidance, self-compassion, rumination, worry, mindfulness, as measured by 14-day daily diary and validated retrospective measures (Self-Compassion Scale-Short Form; Rumination-Reflection Questionnaire; Five Facet Mindfulness Questionnaire; Coping Strategy Scale)
To explore between-group differences in sleep	Subjective sleep	A secondary objective is to explore change in clinical outcome. In future research, we expect that our primary clinical endpoint will be global sleep quality.	Pittsburgh Sleep Quality Index scores (primary); Insomnia Severity Index; Dysfunctional Beliefs About Sleep; Measures for coping with sleep disturbances;

OBJECTIVES	ENDPOINTS	JUSTIFICATION FOR ENDPOINTS	METRIC
			Worry about sleep (secondary)
To explore group differences in other critical clinical outcomes	1. Depressive symptoms 2. Anxiety symptoms 3. Stress	A secondary objective is to explore change in mental health clinical outcomes.	1. PHQ-9 2. PROMIS 6-item anxiety measures 3. Perceived Stress Scale

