## 4.3 JUSTIFICATION FOR INTERVENTION

We will deliver MBSR+PS via video conferencing (i.e., Zoom platform) instead of via in-person sessions for several reasons. First, delivering the intervention remotely affords

us more flexibility and the ability to continue study activities even in the context of potential COVID-19 shelter-in-place orders. Second, pregnant women may have a lower tolerance for risk for attending in-person visits when there are spikes in COVID-19 activity. Third, we want to develop a program that has high potential for scalability and ultimately plan to deliver the intervention remotely in efficacy testing. Thus, the feedback we will get in this feasibility trial will be more relevant. Finally, delivering the intervention remotely is responsive to focus group feedback that women do not want an all in-person intervention.

MBSR will be offered in its typical session format: in 8 weekly sessions with an all-day retreat. The prenatal sleep content will be offered in 6-8 weekly brief sessions designed to be 30 minutes or less. Data will be analyzed on an intent-to-treat basis, and we aim for an average percentage of sessions attended  $\geq 50\%$ .

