#### 6.1.2 ADMINISTRATION AND/OR DOSING

The full-dose MBSR+PS program will consist of:

Standard MBSR:

- 8 weekly sessions
- All day retreat
- Administered by a trained and vetted MBSR instructor via Zoom
- Delivered to heterogeneous groups, including non-pregnant women

Prenatal Sleep Content:

- 6-8 weekly brief sessions ( $\leq$  30 minutes) via Zoom
- Flexibly designed to be delivered 1:1 or to small groups of pregnant women

- Delivered by an instructor with behavioral sleep medicine training

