## 6.4 STUDY INTERVENTION/EXPERIMENTAL MANIPULATION ADHERENCE

As in our previous research, we will use a REDCap database to track and retain participants for follow-up assessments. The tracking file will contain each participant's current status in the study (e.g., enrolled, completed); dates when consent documents are completed, when measures are due, and when measures are completed; and an open text field for comments.

Adherence is operationalized as session attendance and home practice completion. We will enter weekly MBSR+PS attendance into the REDCap database. Participants will be asked to complete a brief daily survey of home practice completion, and home practice completion will be recorded into the REDCap database. Finally, we will track whether participants access and download intervention materials.

To permit intention-to-treat analyses, we will follow participants even if they cease to adhere to the protocol, regardless of condition assignment.

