## 9.3 POPULATIONS FOR ANALYSES

All analyses will be conducted on the intention-to-treat sample defined as all randomized participants. Secondarily, analyses will be conducted on the per-protocol population of MBSR+PS participants who attended  $\geq 50\%$  sessions and all TAU participants.

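### Do the single 50% attendance figure and the pooled 80% retention goal need to be split by component and by arm?

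*Combined protocol and SAP*

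**What the plan says.** Three places use a 50% attendance figure for the MBSR+PS arm. The adherence row of the Section 3 table says "We aim for an average of at least 50% of MBSR and PS supplement" sessions. Section 4.3 restates it: "we aim for an average percentage of sessions attended", again at 50% or more. Section 9.3 defines a secondary population: "analyses will be conducted on the per-protocol population of MBSR+PS participants who attended" at least 50% of sessions, together with all TAU women. None of the three divides the figure between components.

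Section 6.1.2 makes the components unequal in number. MBSR has 8 weekly sessions, with "All day retreat" listed as a further item. The PS content has "6-8 weekly brief sessions".

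Three other provisions bear on the point:
- The initiation metric in Section 3 asks for 85% or more of "MBSR+PS participants to attend at least one session of MBSR and the PS supplement".
- On data capture, Section 6.4 says "We will enter weekly MBSR+PS attendance into the REDCap database".
- The retention goal in Section 3 is 80% or more "of randomized participants to complete endpoint measures". Sections 5.5 and 9.2 carry it as an overall number: 50 randomized, 40 with endpoint data.

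Section 9.1 states no formal hypotheses for the primary objectives, and Section 9.4.2 has every primary endpoint examined descriptively.

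**The concern.** PS is the part of the programme written for pregnant women; MBSR itself is an existing public course. If attendance is one blended percentage, strong MBSR attendance can carry it past 50% while few women use the PS sessions. The per-protocol set could then hold women who received MBSR alone, labelled as having received MBSR+PS. The text also leaves the denominator open, because it does not say whether the retreat is a session or whether 50% is required of each component.

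The retention goal has the same form. One percentage over both arms can be met while the intervention arm loses many more women than TAU, and no section says that retention will be tabulated by arm. Adherence, acceptability and feasibility are the pilot's primary objectives, so a measure that conceals poor uptake of the new component, or differential dropout, would weaken the main product of the study.

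**Working it through.** **1. The plan's own retention figure.** 50 × 0.80 = 40, and 40 / 0.80 = 50. Sections 5.5 and 9.2 reproduce exactly.

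**2. Inputs for attendance.** M = 8 MBSR sessions, or 9 if the retreat counts. P = 6, 7 or 8 PS sessions. T = M + P. All sessions are pooled, which is the reading on which the concern depends. The initiation target is 85%; with 25 women in the arm (1:1 is assumed, since the documents give no ratio) the smallest count reaching it is 22, or 88%.

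- Sessions a woman needs: T/2, rounded up.
- All MBSR and no PS: M/T.
- Mean MBSR attendance needed for the group target with no PS at all: 0.5T/M.
- If 22 of 25 attend exactly one PS session each: mean PS = 0.88/P, and mean MBSR needed = (0.5T − 0.88)/M.

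| M | P | T | Sessions needed | All MBSR, no PS | Mean MBSR needed, no PS | Mean PS, 22/25 attend one | Mean MBSR then needed |
|---|---|---|---|---|---|---|---|
| 8 | 6 | 14 | 7 | 57.1% | 87.5% | 14.7% | 76.5% |
| 8 | 7 | 15 | 8 | 53.3% | 93.8% | 12.6% | 82.8% |
| 8 | 8 | 16 | 8 | 50.0% | 100% | 11.0% | 89.0% |
| 9 | 6 | 15 | 8 | 60.0% | 83.3% | 14.7% | 73.6% |
| 9 | 7 | 16 | 8 | 56.3% | 88.9% | 12.6% | 79.1% |
| 9 | 8 | 17 | 9 | 52.9% | 94.4% | 11.0% | 84.7% |

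The arithmetic behind the concern is right. In all six combinations a woman with no PS session can pass the per-protocol cut. She must, however, attend 7 of 8, 8 of 8, 8 of 9 or 9 of 9 MBSR sessions. The group case needs almost every woman to come to PS once and none to come twice, while MBSR attendance stays at about three-quarters or more.

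**3. What separate thresholds would do.** Take 8 MBSR and 6 PS sessions. A woman with 8/8 MBSR and 2/6 PS has 10/14 = 71%, but fails a 50% PS requirement because 2/6 = 33%. A woman with 4/8 and 3/6 has 7/14 = 50% and passes. The rule would exclude the woman with ten sessions and keep the one with seven. That can be defended, but it is a choice about what counts as an adequate amount of the programme, and it makes the sponsor's target harder to reach.

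**4. Retention.** With 25 per arm, 23 + 17 = 40 meets the goal with 92% in TAU and 68% in MBSR+PS. Under assumed true rates, the chance of at least 40 of 50 is the binomial sum P[Bin(25, p1) + Bin(25, p2) ≥ 40].

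- 80% in both arms: 0.584.
- 90% in TAU and 70% in MBSR+PS: 0.584.

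True overall retention is 80% in both cases, and the pooled goal responds identically. It measures what it says it measures; it was never a test of balance between arms. Requiring 20/25 in each arm would be worse as a feasibility target: with true retention of 80% in both, both arms reach it with probability 0.380.

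**5. What the plan already captures.** The initiation metric cannot be computed without knowing who attended PS. Sections 4.1 and 6.2.1 describe MBSR as courses run by existing programmes and PS as a separate, recorded Zoom series with its own instructor, so attendance arises by component. Section 6.4 has a tracking file with each woman's status and the dates on which measures were completed, which gives retention by arm directly. Reasons for attrition and patterns of missing data are themselves primary endpoints in Section 3.

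**The case for a change.** The best case for a change is that these metrics are what the pilot sets out to test, so their definitions should be fixed before data are seen. The components have different instructors and formats, so divergent attendance is plausible. The 85% initiation target is the only safeguard for PS, and one session satisfies it. Section 6.4 does not state that the components are logged separately. On retention, the missing-data exploration names no arm, and at assumed true rates of 90% and 70% the pooled goal would be met with MBSR+PS below 80% about 40% of the time (0.395). The edits would be short.

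Part of this stands. The denominator is undefined, the retreat is unaddressed, and retention by arm is not pre-specified. A report will need to state the definition it used and should show the two components side by side. But none of that requires a new rule. Tabulating attendance by component and retention by arm is ordinary descriptive practice in a two-arm trial, and nothing in the plan prevents it. The 40% figure rests on invented arm rates, and such a gap would be plain from the arm counts. The Section 3 wording also names both components and can be read as 50% of each, in which case the per-protocol problem does not arise.

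**Conclusion.** No change is needed. The gap is a missing definition that analysts will fill sensibly, and its consequence is small. The affected primary endpoints are descriptive and no progression rule is tied to them. Section 10.1.2 lists general grounds for stopping the study but attaches no attendance or retention figure to them. The per-protocol analysis is secondary, and Section 9.4.3 says the between-group comparisons are not powered and serve as preliminary data.

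The worst cases are real but extreme: no PS with 7/8 to 9/9 MBSR for one woman, or mean PS attendance of 11.0–14.7% with mean MBSR attendance of 73.6–89.0% for the group. Both depend on pooling the sessions, and the group figures also assume 25 women per arm. The one edit that would change a rule, separate 50% thresholds, is a trade-off for the sponsor and not the correction of an error. The pooled retention goal is arithmetically correct and behaves as an overall goal should. This view would change only if attendance were in fact not recorded by component, which the initiation metric makes unlikely.
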